4.1.3.5 ZERO-INFLATED NEGATIVE BINOMIAL MODEL

Number of bleeding events (WHO bleeding scale ≥ 1) and number of significant bleeding events (WHO bleeding scale ≥ 2) will be analyzed using a zero-inflated negative binomial model, which is a mixture model consisting of two components: a negative binomial count model (using the log link) and a binary model (using the logit link) for predicting excess zeros. The model will include the number of bleeding events (see section 4.1.2.2 and 4.1.2.3) as dependent variable, and treatment, the stratification factors and baseline platelet count (continuous) as explanatory factors. An offset term (number of visits with data on bleeding) will be used to take into account the patient exposure. The rate of bleeding over 24 weeks on placebo and efgartigimod will be reported, along with the rate ratio, 95% 2-sided Wald-type CI, and 2-sided p-value.

Missing bleeding assessments strictly after of one of the main intercurrent events will not be imputed. For 'increase of dose and/or frequency of concurrent ITP therapies or start of a new concurrent ITP therapy' and 'initiation of rescue therapy' the whole treatment period should be taken into account. In case of rescue therapy, the bleeding events will not be imputed for 4 weeks strictly after the initiation of the therapy (the initiation of the therapy is the start date/time of the administration of the first rescue treatment for that occurrence).

SGS	SGS Statistical Analysis Plan	
ARGX-113-1801	Final analysis	Final 1.0 of 28MAR2022

Missing bleeding assessments for other reasons than the main intercurrent events will be imputed as described in section 4.1.2.5 (approach 3).

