The number of bleeding events per patient (assessed using the WHO bleeding scale; where WHO scale ≥1 at any visit is considered a new bleeding event) will be analyzed using a zero-inflated negative binomial model. This model will account for the large expected number of patients with zero bleeding events. It is a mixture model consisting of 2 components: a

argenx BVBA Confidential Page 83 of 162

negative binomial count model and a binary model for predicting excess zeros. The model will consist of the number of events as the dependent variable and of randomized treatment, the stratification variables (history of splenectomy; receiving concurrent ITP therapies at baseline), and baseline platelet count as independent variables. An offset term will be used to allow for patient exposure. Both the count model, using the log link, and the binary model, using the logit link, will contain the same independent variables. The probability of no bleeding will be estimated for each randomized treatment group. A Wald test will be used to test the null hypothesis that the log of the bleeding rate ratio on placebo and efgartigimod is equal to zero against the alternative that it is different from zero. The rate of bleeding over 24 weeks on placebo and efgartigimod will be provided, along with the rate ratio, 95% 2-sided Wald-type CI, and 2-sided p-value. Missing bleeding assessments for reasons of 1 of the main intercurrent events will not be imputed, but the offset term will be adapted accordingly to reflect the assessment period until the occurrence or start of the intercurrent event. Incidence of bleeding will also be summarized descriptively by visit. Severity of bleeding will be summarized descriptively by visit. In addition, a summary of within-subject maximum severity will be provided.

The primary endpoint analysis will act as gatekeeper for the testing of the key secondary endpoints. Subject to meeting statistical significance for the primary endpoint, the key secondary endpoints will be analyzed using a fixed-sequence testing procedure to maintain the overall type I error rate at 5%. The type I error rate of each individual test will be 5%, but the test will only be conducted if the analysis for all previous endpoints in the pre-defined hierarchy resulted in a p-value <0.05. The order in the testing hierarchy of the key secondary endpoints is as follows:

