Derivation: total number of analysis visits for which WHO bleeding scale ≥ 1 . The overall score of the bleeding events per analysis visit will be used, calculated as the maximum bleeding scale over the different body systems available per analysis visit. The data will be used as is, without taking into account intercurrent events (treatment policy strategy). Missing bleeding assessments after one of the main intercurrent events will not be imputed. For 'increase of dose and/or frequency of concurrent ITP therapies or start of a new concurrent ITP therapy' and 'initiation of rescue therapy' the whole treatment period should be taken into account. In case of rescue therapy, the bleeding events will not be imputed for 4 weeks strictly after the initiation of the therapy (the initiation of the therapy is the start date/time of the administration of the first rescue treatment for that occurrence). Missing values for reasons other than the main intercurrent events, will be imputed as described in section 4.1.2.5 (approach 3).

4) Proportion of patients achieving platelet counts of at least 50×109/L for at least 6 of the 8 visits between weeks 17 and 24 of the study in the overall population.

Derivation: A patient is considered a responder if he/she shows platelet counts of at least 50×10^9 /L for at least 6 of the 8 analysis visits between weeks 17 and 24 of the study. Intercurrent events will be handled with the same composite variable strategy as described in section 4.1.2.1. Missing values not due to intercurrent events will be handled as described in section 4.1.2.5 (approach 1).

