Derivation: total number of analysis visits during the treatment phase with platelet counts of $\ge 30 \times 10^9$ /L and (platelet count – baseline platelet count) $\ge 20 \times 10^9$ /L. Platelet count after one of the main intercurrent events will be handled in the same way as for extent of disease control (section 4.1.2.2). Missing values not due to intercurrent events will be handled as described in section 4.1.2.5 (approach 1), but imputing with $\ge 30 \times 10^9$ /L / $< 30 \times 10^9$ /L and not with $\ge 50 \times 10^9$ /L / $< 50 \times 10^9$ /L. In the same way, if (platelet count – baseline platelet count) $\ge 20 \times 10^9$ /L for the previous and the next analysis visit, (platelet count – baseline platelet count) will imputed with $\ge 20 \times 10^9$ /L, otherwise with $< 20 \times 10^9$ /L.

The above will be repeated for the selection of patients where baseline platelet count $<15 \times 10^{9}$ /L.

b) $\geq 30 \times 10^9/L$ and at least $20 \times 10^9/L$ greater than the baseline value, where baseline platelet count $< 15 \times 10^9/L$.

10) Mean changes from baseline for:

Missing values will not be imputed.

Number of significant bleeding events where WHO bleeding scale ≥ 2 at any visit.

Derivation: total number of analysis visits for which WHO bleeding scale ≥ 2 . The overall score of the bleeding events per analysis visit will be used, calculated as the max bleeding scale over the different body systems available per analysis visit. The data will be used as is, without taking into account intercurrent events (treatment policy strategy). Missing bleeding assessments after one of the main intercurrent events will not be imputed. For 'increase of dose and/or frequency of concurrent ITP therapies or start of a new concurrent ITP therapy' and 'initiation of rescue therapy' the whole treatment period should be taken into account. In case of rescue therapy, the bleeding events will not be imputed for 4 weeks strictly after the initiation of the first rescue treatment for that occurrence). Missing values for reasons other than the main intercurrent events, will be imputed as described in section 4.1.2.5 (approach 3), but imputing as "scale >=2" instead of "bleeding" and as "bleeding scale<2" instead of "no bleeding".

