14) Proportion of patients achieving platelet counts of at least $\geq 50 \times 10^9$ /L for at least 8 out of 12 visits between weeks 13 and 24 of the study.

Derivation: a patient is considered a responder if he/she shows platelet count of at least 50×10^9 /L for at least 8 of the 12 analysis visits between weeks 13 and 24 of the study. Platelet count after one of the main intercurrent events will be handled in the same way as for extent of disease control (section 4.1.2.2). Missing values not due to intercurrent events will be handled as described in section 4.1.2.5 (approach 1).

15) Proportion of patients with an IWG-Complete response¹².

Derivation: a patient is considered a responder if he/she shows platelet count of at least 100×10^9 /L and the absence of bleeding events (WHO=0) for at least 2 separate,

SGS	Statistical Analysis Plan	
ARGX-113-1801	Final analysis	Final 1.0 of 28MAR2022

consecutive occasions which are at least 7 days apart (in case of missing visits (phantom records), the target date will be used). Platelet count after one of the main intercurrent events will be handled in the same way as for extent of disease control (section 4.1.2.2), but imputing $<100\times10^9$ /L instead of $<50\times10^9$ /L. If platelet count $\ge100\times10^9$ /L for the previous and the next analysis visit, the platelet count will be imputed with $\ge100\times10^9$ /L, otherwise with $<100\times10^9$ /L. Missing bleeding assessments after one of the main intercurrent events will not be imputed. For 'increase of dose and/or frequency of concurrent ITP therapies or start of a new concurrent ITP therapy' and 'initiation of rescue therapy' the whole treatment period should be taken into account. In case of rescue therapy, the bleeding events will not be imputed for 4 weeks strictly after the initiation of the therapy (the initiation of the therapy is the start date/time of the administration of the first rescue treatment for that occurrence). Missing bleeding assessments for other reasons than the main intercurrent events will be imputed as described in section 4.1.2.5 (approach 3)

16) Proportion of patients with an IWG-Response¹².

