4.1.2.5 IMPUTATION

Missing data (platelet counts) for other reasons than the main intercurrent events will be imputed as follows:

- Approach 1: if platelet count $\geq 50 \times 10^{9}/L$ for the previous and the next analysis visit, and the previous and next analysis visit are in the treatment phase, the platelet count will be imputed with $\geq 50 \times 10^{9}/L$, otherwise with $< 50 \times 10^{9}/L$.
- Approach 2: all missing data will be imputed with $<50\times10^{9}$ /L. This will only be used as sensitivity analysis for the primary endpoint and the first key secondary endpoint.

Intermittent missing data (WHO bleeding assessment) for other reasons than the main intercurrent events will be imputed as follows:

• Approach 3: If no bleeding event for previous and next analysis visit (which can enclose several successive missing bleeding assessments), and the previous and next analysis visit are in the treatment phase, impute with no bleeding event, otherwise impute with bleeding event. No imputation will be done after the last available bleeding assessment in the treatment phase.

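### Bleeding model: the SAP does not say that visits filled by imputation count in the offset, so on its plain wording imputed bleeds have no exposure

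*SAP*

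**What the plan says.** SAP 4.1.2.2 counts, for each patient, the analysis visits graded 1 or higher on the WHO scale. SAP 4.1.2.3 does the same for grade 2 or higher. SAP 4.1.3.5 models both counts with a zero-inflated negative binomial model and reports 24-week rates and their ratio. The exposure rule is: "An offset term (number of visits with data on bleeding) will be used to take into account the patient exposure".

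The same section sends missing assessments that are not due to a main intercurrent event to approach 3 in SAP 4.1.2.5. That rule looks at the visits on either side of a gap. If both are bleed-free it says "impute with no bleeding event, otherwise impute with bleeding event". Nothing is imputed after the last available assessment.

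On intercurrent events, Protocol 8.4.2 says: "Missing bleeding assessments for reasons of 1 of the main intercurrent events will not be imputed, but the offset term will be adapted accordingly" and continues "to reflect the assessment period until the occurrence or start of the intercurrent event". The SAP instead takes a treatment-policy approach. After rescue or an increase in ITP therapy, SAP 4.1.3.5 says that "the whole treatment period should be taken into account". SAP 6.1, which lists departures from the protocol, does not mention this.

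The covariates are treatment, the two stratification factors and continuous baseline platelet count. A baseline WHO bleeding category is derived in SAP 3.3.2 but is not in the model.

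**The concern.** A rate needs the same visits in its numerator and denominator. Approach 3 puts filled visits into the numerator. A missing assessment is, in ordinary words, not a visit with data, so the offset would leave the same visits out. Each arm's rate would then be inflated by a factor that grows with its share of intermittent gaps, and arms with different shares would be inflated differently.

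The test is third among the key secondary endpoints and gates the fourth (Protocol 8.4.2, SAP 4.1.3.1). SAP 1.8 assigns the bleeding endpoint to independent double programming, and two programmers could both follow this text and build different offsets. No missing-data sensitivity analysis would expose the difference. SAP 4.1.2.5 limits approach 2 to the primary and first key secondary endpoints, and for bleeding SAP 4.1.3 offers only the per-protocol repeat.

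**Working it through.** **Inputs.** The count, offset and imputation rules come from SAP 4.1.2.2, 4.1.2.5 and 4.1.3.5. There are 24 weekly post-baseline analysis visits (SAP 2.2.4), so no patient can have more than 24 events in 24 weeks. The documents give no bleeding rate, gap rate or power for this test, so there is no figure to reproduce, and every probability below is assumed.

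**One patient.** Rate per 24 weeks = 24 × (observed + imputed bleeds) / offset.

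- 20 bleeds at 20 observed visits, 4 imputed bleeds: 24 × 24/20 = 28.8 if the offset is observed visits; 24 × 24/24 = 24.0 if filled visits are included.
- 5 bleeds at 22 observed visits, 2 imputed bleeds: 24 × 7/22 = 7.64, against 24 × 7/24 = 7.00.

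**One arm.** Let p be a common weekly bleeding probability and m the share of visits in intermittent gaps, with an observed visit on each side of every gap. Approach 3 fills a gap as bleeding with probability 1 − (1 − p)². At p = 0.30 this is 1 − 0.49 = 0.51.

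- Literal offset (observed visits only): [(1 − m)p + 0.51m] / (1 − m).
- Aligned offset (observed plus filled visits): (1 − m)p + 0.51m.

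At m = 0.05 these give 0.3105/0.95 = 0.3268 and 0.3105. At m = 0.10 they give 0.3210/0.90 = 0.3567 and 0.3210. At 10% gaps the 24-week rate is therefore 24 × 0.3567 = 8.56 (literal) or 24 × 0.3210 = 7.70 (aligned), against a true 24 × 0.30 = 7.20.

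**Rate ratio, efgartigimod to placebo, with no treatment effect (p = 0.30):**

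| Gaps, efgartigimod / placebo | Literal | Aligned |
|---|---|---|
| 10% / 10% | 1.000 | 1.000 |
| 5% / 10% | 0.916 | 0.967 |
| 10% / 5% | 1.091 | 1.034 |
| 3% / 5% | 0.966 | 0.986 |
| 2% / 3% | 0.983 | 0.993 |

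The two columns differ by the factor (1 − m placebo)/(1 − m efgartigimod), for example 0.90/0.95 = 0.947. For gaps of 5% / 10% and p from 0.05 to 0.50, the literal ratio is 0.91 to 0.92 and the aligned ratio 0.96 to 0.98. Aligning the offset does not bring the ratio fully to 1, because approach 3 fills gaps pessimistically. Counting observed visits only gives 1.00.

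**Intercurrent events.** Take a patient who stops treatment at week 12 for an adverse event and attends 11 of the 12 later visits. Protocol 4.4.2 keeps such patients on weekly visits. On one reading of Protocol 8.4.2 the exposure is 12 weeks; under the SAP it is 12 + 11 = 23 visits.

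**Baseline bleeding.** In a simplified simulation with assumed inputs (250 replicates per case), adding baseline bleeding (yes/no) to the count part lowered the standard error from 0.130 to 0.124 and from 0.157 to 0.145 at the two larger between-patient spreads, and hardly at all at the smallest. Rejection under no effect stayed near or below 5%. In a separate simulation with a true ratio of 0.65, no baseline bleeder had a zero count in 48 to 75% of replicates. An unpenalised zero part would separate in those data.

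**The case against.** **The other reading of the offset is coherent.** The SAP does not say observed visits. Once a gap is filled, the visit has a bleeding value, and the visits without data are then those never filled. SAP 4.1.2.4 carries records for missed visits ("in case of missing visits (phantom records), the target date will be used"), which points the same way. A count that can exceed its own exposure is unlikely to have been intended. The code for this model (SAP 9.1.4) is not readable in the public copy and may settle the matter. All of this stands, and it is why the point is an ambiguity in the readable text and not an established error.

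**The effect may be small.** Gaps after an intercurrent event and trailing gaps are not imputed, the analysis windows are contiguous and accept unscheduled assessments, and Protocol Appendix 4 allows bleeding assessment at home or by video. This also stands.

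**A reader might infer that the test's type I error is inflated.** The documents do not support that. Simulated rejection under no effect reached 8.0% (gaps 5% / 10%) and 20.2% (5% / 15%) with the literal offset, but only because unequal gaps were assumed between the arms of a double-blind trial on one visit schedule. With equal 10% gaps it was 4.9%. These figures describe the assumed scenarios, not the plan.

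**A reader might also infer that the protocol drops bleeds observed after an intercurrent event.** It does not say so. Its offset sentence concerns missing assessments, and the SAP's treatment-policy rule largely answers the question. What remains is an unlisted difference in wording.

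**Conclusion.** The point holds as a gap in specification. An alpha-controlled test has an offset that can be built in two ways, and on the plain wording imputed bleeds carry no exposure. The certain consequence of that reading is inflated 24-week rates in any arm with imputed visits. By the formulas above, the literal rate exceeds the aligned rate by the factor 1/(1 − m): 5.3% at m = 5% and 11.1% at m = 10%. A shift in the rate ratio is conditional on unequal intermittent gaps, and its size (0.916 against 0.967 in the illustration) rests wholly on assumed rates and gap shares.

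The missing baseline covariate is an opportunity, not an error: protocol and SAP agree on the covariates they list. Its gain depends on how strongly baseline bleeding predicts later bleeding.

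**What to change.** (a) In SAP 4.1.3.5, state that the offset is the log of the number of visits that contribute to the count, observed plus filled by approach 3. Apply this to both the grade 1 or higher and the grade 2 or higher counts. Add a sensitivity analysis that counts observed visits only, with log(observed visits) as offset. That analysis assumes that a patient's missed visits bleed like the attended ones; approach 3, kept as the main rule, covers the pessimistic case.

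(b) Add baseline WHO bleeding (yes/no) to the count part only. It costs one parameter. Leave it out of the unpenalised zero part because of separation. Protocol 8.4.2 gives both parts the same independent variables, so this change also belongs in SAP 6.1.

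(c) List in SAP 6.1 that exposure is the visits with data over the whole treatment period, under the treatment-policy rule, and that this replaces the Protocol 8.4.2 wording on the period until the intercurrent event. Name early discontinuation explicitly along with the other two events.

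The cost is a few sentences and some code, with no new data. The changes should be fixed before unblinding.

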4.1.3.6 MIXED MODEL FOR REPEATED MEASUREMENTS

For changes from baseline (see section 4.1.2.3), between treatment group differences will be analyzed by means of Mixed Models for Repeated Measurements (MMRM). All available data will be included. Data after one of the main intercurrent events will be imputed with the baseline value/score. Other (missing) values will not be imputed. The model will include treatment, analysis visit and treatment by visit interaction terms as fixed effects, with baseline value and stratification factors as covariates. Only analysis visits within the treatment phase will be considered. Within-patient correlation will be modeled by assuming an unstructured covariance matrix for the error terms. If the model does not converge upon using UN, the following covariance structures will be tested for convergence (in order): toeph, arh(1), csh, toep, ar(1) and cs. Least square (LS) means for placebo and efgartigimod will be reported, along with the difference in LS means, 95% 2-sided CI, and 2-sided p-value.

This model will be applied for the mean changes in platelet count levels, PRO (FACIT-Fatigue, FACT-Th6) and QoL (SF-36: 8 subdomain scores, P-CS and M-CS).

4.1.3.7 Cox Proportional Hazards Regression

The Cox proportional hazard model will be used to calculate the estimate of the hazard ratio (HR) and 95% confidence interval for the treatment effect of the extent of disease control as complementary analysis for the first key secondary endpoint (see section 4.1.2.2), and the time to platelet count response (see section 4.1.2.3).

The model will include treatment as fixed effects, with baseline platelet level and stratification factors as covariates. The HR for efgartigimod vs. placebo will be provided, along with the associated 95% 2-sided Wald-type CI and 2-sided p-value.

4.1.4 Subgroup analyses for efficacy

Subgroups are defined based on the following categorizing factors:

- Dosing frequency (weekly versus bi-weekly): as derived in section 3.6.2
- History of splenectomy (yes versus no)
- Receiving concurrent ITP therapies at baseline (yes versus no)
- Baseline platelet count: $(<15\times10^{9}/L, \ge 15\times10^{9}/L)$
- Time since diagnosis (chronic versus persistent)
- Number of prior ITP therapies (<3 prior therapies, \geq 3 prior therapies)
- Sex at birth (male, female)
- Region (United States / Japan / Europe / rest of the world)
- Age category (18-<65 years; 65-<75 years; \geq 75 years)
- Race (American Indian or Alaska Native, Asian, Black or African American, White, Other)
- Ethnicity category (Japanese versus non-Japanese)
- Weight category at baseline (<50 kg, 50-<75 kg, 75 <120 kg, $\ge 120 \text{ kg}$)

SGS	Statistical Analysis Plan	
ARGX-113-1801	Final analysis	Final 1.0 of 28MAR2022

- Prior Rituximab (yes versus no): as defined in section 3.5.2
- Prior TPO-RA (yes versus no): as defined in section 3.5.2

Note that subgroup categories with less than 5 patients (overall) will not be included in the tables.

Subgroup analyses will be performed on the following efficacy endpoints:

- Sustained platelet count response (week 19 24) in the overall population
- Extent of disease control (first key secondary endpoint) in the overall population (all subgroup analyses except dosing frequency [weekly versus bi-weekly]).

4.2 **PHARMACOKINETICS**

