4.1.3 Statistical analysis

Wherever the stratification factors will be used in the efficacy analyses, the actual values of these will be used and not the ones coming from the randomisation.

Summary statistics will be provided in terms of actual values and changes from baseline for platelet count in the chronic and the overall FAS population. All analysis visits as expected per SoA (including the follow-up phase) will be shown.

Frequency tabulations will be provided of the percentage of responders with sustained platelet count (primary endpoint) in chronic patients and overall and by stratification factors (receiving concurrent ITP therapies at baseline [yes/no], history of splenectomy [yes/no]) and baseline platelet count. The table in the overall population will be repeated by subgroup and ADA patient classification. The table for chronic patients will be repeated for the complementary analysis using the treatment policy strategy.

Frequency tabulations will be provided of the percentage of responders with sustained platelet count (different definitions excluding primary endpoint) and of the percentage of responders with overall response (week 1 - 24 and week 1 - 12) in the overall population. Frequency tabulations will also be provided for all different response definitions for platelet count as defined in section 6.1. The response rates and differences in response rate (efgartigimod-placebo) will be shown together with the 95% Agresti-Min¹⁴ confidence limits. The tabulation of the sustained platelet count response (week 19 - 24) in the overall population will be repeated by subgroup.

For the different endpoints on extent of disease control, summary statistics will be provided on the number of cumulative weeks of disease control in the overall population. For the first key secondary endpoint extent of disease control will also be summarized for the chronic population and by stratification factors and baseline platelet count. This first key secondary endpoint summary table for the overall population will also be repeated by subgroup. Furthermore, a table with Kaplan-

SGS	Statistical Analysis Plan	
ARGX-113-1801	Final analysis	Final 1.0 of 28MAR2022

Meier (KM) estimates will be displayed by randomized treatment arm for the first key secondary endpoint (complementary analysis).

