14.2.1.2.2	Platelet Count: Sustained Platelet Count Respo (≥50×10^9/L (week 19 to 24)) in Patients with ITP – Cochran-Mantel-Haenszel - PP-Chronic	onders Chronic	PP- chronic
14.2.1.2.3	Platelet Count: Sustained Platelet Count Respondence (≥50×10^9/L (week 19 to 24)) in Patients with ITP – Cochran-Mantel-Haenszel Complement (Treatment Policy Strategy)- FAS-Chronic	onders Chronic ary Analysis	FAS- chronic
14.2.1.2.4	Platelet Count: Sustained Platelet Count Response (≥50×10^9/L (week 19 to 24)) in Patients with ITP – Cochran-Mantel-Haenszel - Sensitivity	onders Chronic Analysis	FAS- chronic
14.2.1.3	Platelet Count: Sustained Platelet Count Respo (≥50×10^9/L (week 19 to 24)) in Patients with ITP – Exact Conditional Logistic Regression – chronic	onders Chronic - FAS-	FAS- chronic
14.2.1.4	Platelet Count: Descriptive Statistics of Actual Changes from Baseline (x10^9/L) in Patients v ITP	Values and vith Chronic	FAS- chronic
14.2.1.5.1	Platelet Count: Sustained Platelet Count Responses $(\geq 50 \times 10^{9}/L \text{ (week 19 to 24)})$ in Patients with	onders Chronic	FAS- chronic

SGS	Statistical Analysis Plan		
ARGX-113-1801	Final analysis	Final 1.0 of	28MAR2022
	ITP – Frequency Tabulation by Stratification F Baseline Platelet Count and Overall	actor,	
14.2.1.5.2	Platelet Count: Sustained Platelet Count Respon (≥50×10^9/L (week 19 to 24)) in Patients with ITP – Frequency Tabulation by Stratification F Baseline Platelet Count and Overall – Complem Analysis (Treatment Policy Strategy)	nders Chronic actor, nentary	FAS- chronio
14.2.1.6	Platelet Count: Sustained Platelet Count Responses $(\geq 50 \times 10^{9}/L \text{ (week 19 to 24))}$ in the Overall Po Cochran-Mantel-Haenszel	nders opulation –	FAS
14.2.1.7.1	Platelet Count: Sustained Platelet Count Respon (≥50×10^9/L (week 19 to 24)) in the Overall Po Frequency Tabulation by Stratification Factor, Platelet Count and Overall	nders opulation – Baseline	FAS
14.2.1.7.2	Platelet Count: Sustained Platelet Count Respon (≥50×10^9/L (week 19 to 24)) in the Overall Po Frequency Tabulation by Stratification Factor a by Baseline Platelet Count	nders opulation – and Overall	FAS
14.2.1.7.3	Platelet Count: Sustained Platelet Count Respon (≥50×10^9/L (week 19 to 24)) in the Overall Po Frequency Tabulation by Stratification Factor, Platelet Count and Overall by Dosing Frequence	nders opulation – Baseline zy	FAS

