14.2.1.37	Platelet Count: Percent Change from Baseline in Count by ADA Patient Classification	n Platelet	FAS
14.2.1.38	Platelet Count: Percent Change from Baseline in Count by NAb Patient Classification	n Platelet	FAS
14.2.2.1.1	Extent of Disease Control (≥50x10^9/L): Stratif Whitney Analysis in Patients with Chronic ITP Chronic	ied Mann- – FAS	FAS- chronic
14.2.2.1.2	Extent of Disease Control (≥50x10^9/L): Stratif Whitney Analysis in Patients with Chronic ITP Chronic	ied Mann- – PP	PP- chronic
14.2.2.1.3	Extent of Disease Control (≥50×10^9/L): Stratif Whitney Complementary Analysis (Treatment F Strategy) in Patients with Chronic ITP – FAS C	ied Mann- Policy hronic	FAS- chronic
14.2.2.1.4	Extent of Disease Control (≥50×10^9/L): Stratif Whitney Sensitivity Analysis in Patients with C – FAS Chronic	ied Mann- hronic ITP	FAS- chronic

SGS	Statistical Analysis Plan		
ARGX-113-1801	Final analysis	Final 1.0 of	28MAR2022
14.2.2.2	Extent of Disease Control (≥50×10^9/L): Comp Analysis: Cox Proportional Hazards Regression Patients with Chronic ITP	lementary Model in	FAS- chronic
14.2.2.3	Extent of Disease Control (≥50×10^9/L): Kapla Estimates in the Overall Population	n Meier	FAS
14.2.2.4	Extent of Disease Control (≥50×10^9/L): Descr Statistics of Cumulative Number of Weeks of D Control by Stratification Factor, Baseline Platel and Overall in Patients with Chronic ITP	iptive Disease et Count	FAS- chronic
14.2.2.5	Extent of Disease Control (≥50×10^9/L): Stratit Whitney Analysis in the Overall Population	fied Mann-	FAS
14.2.2.6.1	Extent of Disease Control (≥50×10^9/L): Descr Statistics of Cumulative Number of Weeks of D Control by Stratification Factor and Overall in t Population	iptive Disease he Overall	FAS
14.2.2.6.2	Extent of Disease Control (≥50×10^9/L): Descr Statistics of Cumulative Number of Weeks of D Control in the Overall Population by Baseline P Count	iptive Visease latelet	FAS
14.2.2.6.3	Extent of Disease Control (≥50×10^9/L): Descr Statistics of Cumulative Number of Weeks of D Control in the Overall Population by Dosing Fre	iptive Disease equency	FAS
14.2.2.6.4	Extent of Disease Control (≥50×10^9/L): Descr Statistics of Cumulative Number of Weeks of D Control in the Overall Population by Number of Therapies	iptive Disease f Prior ITP	FAS
14.2.2.6.5	Extent of Disease Control (≥50×10^9/L): Descr Statistics of Cumulative Number of Weeks of D Control in the Overall Population by Time Sinc	iptive Disease e Diagnosis	FAS

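### Dosing frequency is set after randomisation by the patient's own platelet counts, so the SAP should rule out efgartigimod-placebo contrasts within it for sustained response

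*SAP*

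**What the plan says.** SAP 4.1.4 names the factor as "Dosing frequency (weekly versus bi-weekly): as derived in section 3.6.2". It applies it to sustained response (weeks 19-24) in the overall population. For the other subgroup endpoint, extent of disease control, the same section specifies "all subgroup analyses except dosing frequency [weekly versus bi-weekly". Every other factor in the 4.1.4 list is known at baseline.

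SAP 3.6.2 derives the label from dosing at visits 14 to 17, and only for patients still receiving study drug at visit 17 or later. Its possible values are q2w, weekly and 'Unknown'.

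SAP 4.1.3 has two adjoining paragraphs on frequency tables. The first covers the primary-endpoint definition of response, describes percentages of responders, and says "The table in the overall population will be repeated by subgroup and ADA patient classification". The second opens with the other response definitions, says that "differences in response rate (efgartigimod-placebo) will be shown together with the 95" per cent Agresti-Min limits, and follows this directly with "The tabulation of the sustained platelet count response (week 19 - 24) in the overall population will be repeated by subgroup".

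The table list in SAP 8.1 includes Table 14.2.1.7.3, sustained response by dosing frequency on the full analysis set. It also includes Table 14.2.2.6.3, extent of disease control by dosing frequency: "Control in the Overall Population by Dosing Fre" (the end of the word is broken in the extracted text).

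**The concern.** A between-arm comparison within a subgroup keeps the protection of randomisation only if membership could not have been influenced by treatment. Here membership results from treatment. A placebo patient on q2w reached high counts without efgartigimod; an efgartigimod patient on q2w may have reached them because of it. The two weekly groups are likewise what remains of each arm after different selection. Because the sorting variable is an earlier reading of the endpoint variable, the link between label and outcome is close.

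If the table shows a difference with confidence limits for each level, a reader may take it as the treatment effect under weekly or under q2w dosing. It estimates neither. No confirmatory conclusion depends on it, but the display could be quoted in that sense.

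**Working it through.** There is no planned figure to reproduce for this point, so the check is mainly a comparison of passages.

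**1. Is the factor post-randomisation and driven by the outcome variable?** Protocol 5.4.1 moves a patient from weekly to q2w after repeated counts of at least 100×10⁹/L. It moves the patient back after two consecutive counts below 100, one count below 30, or rescue therapy. Protocol 4.5 adds resumption on q2w after counts above 400. Changes can occur at visits 5 to 16; the regimen is then fixed. SAP 4.1.2.1 defines response as counts of at least 50×10⁹/L at 4 or more of the 6 analysis visits in weeks 19-24. So the answer is yes.

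**2. Who is left out?** Under SAP 3.6.2, patients not dosed at or after visit 17 have no label. Under SAP 4.1.2.1, those among them who stopped for lack of efficacy or an adverse event without a sustained response count as non-responders. Weekly plus q2w is therefore less than the full analysis set wherever anyone stopped before visit 17, and the loss need not be equal between arms.

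**3. Is a difference planned in Table 14.2.1.7.3?**

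| Evidence | Points to |
|---|---|
| Title layout (by stratification factor, baseline platelet count and overall) matches the first paragraph of 4.1.3 | Percentages only |
| Table 14.2.1.7.12, by ADA classification, is in the same series; only the first paragraph mentions ADA | Percentages only |
| In the second paragraph, the repeat by subgroup comes straight after the differences with limits | Difference shown |
| The 14.2.1.7 series is the only listed set giving sustained response by subgroup, so both sentences must refer to it | Unresolved |

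The text does not settle it.

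**4. Would a row with no comparator be suppressed?** The rule is "Note that subgroup categories with less than 5 patients (overall) will not be included in the tables". It counts both arms together, so 5 efgartigimod and 0 placebo patients on q2w would still print. With 117 + 39 = 156 patients randomised 2:1, the arms are 104 and 52. The documents give no placebo share on q2w. If it were 1% to 5%, the expected number is 52 × 0.01 = 0.5 to 52 × 0.05 = 2.6, and the chance of none is 0.99^52 = 0.59 to 0.95^52 = 0.07 (patients taken as independent). If it were 10% to 15%, the number is 5.2 to 7.8. Protocol 6.8.1 allows TPO-RA dose changes at label thresholds, so a higher placebo share cannot be excluded.

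**5. Illustration of the structure, not of size.** I simulated the switching rules with 400,000 patients per arm. Counts were log-normal with median 25×10⁹/L and log-scale SDs of 0.6 between and 0.4 within patients. Rescue, drop-out and the rule for counts above 400 were left out. All these parameters are assumptions.

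| Assumed drug effect | All patients (points) | Weekly | q2w |
|---|---|---|---|
| None | 0.0 | 0.0 | -0.5 |
| In half of patients, lasting | 36.5 | 20.9 | 1.1 |
| In half of patients, ending about week 16 | 0.0 | -3.4 | -73.6 |

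With no effect, both rows are close to zero. In the two scenarios with an effect, neither row recovers the randomised difference. Drop-out, which was left out, removes non-responders from the weekly row and can move it the other way.

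**The case against.** The strongest reply is that the contrast may not be planned at all. Table 14.2.1.7.3 fits the paragraph that promises only percentages, and on that reading most of the fix is already in place. This stands as a limit on confidence. It does not remove the point, because the second paragraph can equally be read as adding differences and limits, and unannotated arm percentages side by side still invite the comparison.

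It can also be said that weekly and q2w dosing are part of the design, that the regimen is fixed before week 19, and that describing response by regimen is legitimate. That is correct for description within an arm. It does not make the arms comparable within a level.

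Three stronger readings are tempting but not supported. A reader might infer that the weekly row must understate the effect, because good responders leave it; but patients who stop early leave it too, so the direction is unknown. A reader might take the ADA tables in SAP 4.4.3, restricted to efgartigimod patients, as a precedent for avoiding between-arm display; but Table 14.2.1.7.12 puts ADA classification in the same full-analysis-set series, so the precedent is not clean. A reader might infer that the main results are compromised; the factor does not enter the testing sequence in SAP 4.1.3.1.

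**Conclusion.** The point holds in a limited form. Dosing frequency is a post-randomisation factor determined by the variable that defines the endpoint, so any efgartigimod-placebo difference in sustained response within the weekly or q2w level is not like-for-like, and the levels omit unlabelled patients. This follows from the protocol and SAP text without numerical assumptions; the distortion disappears only if the drug has no effect on counts.

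Its size cannot be given: response rates are redacted, and the documents state neither q2w shares nor unlabelled shares. Whether the contrast will be displayed is ambiguous, which is why confidence is medium. Severity is minor: the table is descriptive and outside the alpha-controlled hierarchy, and the primary and key secondary tests are unaffected.

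Separately, and without any inference, SAP 4.1.4 excludes dosing frequency for extent of disease control while SAP 8.1 still lists Table 14.2.2.6.3. These two places contradict each other.

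**What to change.** - In SAP 4.1.3 and 4.1.4, state that dosing frequency is excluded from between-arm subgroup contrasts for sustained response, as 4.1.4 already excludes it for extent of disease control.
- Show Table 14.2.1.7.3 as number of patients and response rate within each arm, with no difference and no limits. Add a footnote that the factor is determined after randomisation, and give the number of unlabelled or 'Unknown' full-analysis-set patients per arm.
- Reconcile 4.1.4 with Table 14.2.2.6.3; removing that table would match 4.1.4.
- Leave the 3.6.2 derivation unchanged, since the PK and IgG tables (SAP 4.2.3 and 4.3.3) also use it.

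The cost is a few lines of SAP wording, one table shell with a footnote, and one list entry. No new data and no re-derivation of the label are needed.
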